5.5 Derived and Computed Variables

The definitions of key derived variables will be provided in a separate dataset specifications document. For example, age will be calculated as the integer portion of

$$\frac{\text{Date of informed consent} - \text{Date of birth}}{365.25}.$$

Primary and secondary outcome definitions are described in Section 7.1.

All derived variables used in analyses will be dual-coded by a second statistician to promote quality and minimize error; see also Section 5.6.

5.6 Independent Review

All statistical analyses for primary reporting of trial results will be independently verified through dual programming. Two statisticians will each program all datasets and analyses for the DSMB reports and the primary manuscript(s) and the results will be compared. This process will begin at the analysis design stage and will continue through writing of abstracts and manuscripts for primary analyses.

Additional analyses for secondary abstracts or manuscripts will use a second statistician conducting at least code review, if not dual programming.

6 INTERIM ANALYSES

6.1 Frequency of and Timepoints for Interim Analysis

The only planned interim analyses are for reports to be provided to the Data and Safety Monitoring Board (DSMB). The frequency of the interim analyses for the DSMB will be per the DSMB charter.

The DSMB will be provided with summaries of adverse events (AEs) and serious adverse events (SAEs); some of the AE and SAE summaries coincide with safety outcome analyses described in Section 7.6.1. Adverse events will be summarized as to their seriousness, expect-edness, relatedness to study, and severity. Overall summaries of the ITT population may be provided for the open session of DSMB meetings, but summaries by treatment arm for the ITT population will be limited to the closed session for interim analyses. Even overall summaries might be limited to the closed session of interim DSMB reports to promote the blindedness of study results for the principal investigator until all patients have had time for all study-prescribed follow-up.

The closed session will also present adverse event summaries for the subset of ITT subjects who were randomized to the pAF treatment arm AND received at least one study-administered pAF injection.

6.2 Stopping Rules for Interim Efficacy Analysis

There is no stopping rule for interim analysis of the secondary efficacy outcome, either for demonstrated efficacy or for futility. The study is not adequately powered to spend alpha early.

6.3 Subgroups in the Interim Analysis

No subgroup analyses are planned for the interim analysis. Nonetheless, the DSMB has the prerogative to request such subgroup analyses as they deem appropriate.

6.4 Blinding in the Interim Analysis

Any interim analyses for the DSMB reports will be limited by only including summaries by treatment arm in the closed session. Attendance at the closed session will be limited to the DSMB members and the DCC biostatisticians. Actual treatment designations will be used in the closed session report.

7 PLANNED ANALYSES

7.1 Description of Subject Characteristics

The primary results will include a summary of the following baseline measures, by randomized treatment arm and overall:

- Sex (male, female)
- Race (white, non-white)
- Ethnicity (Latinx, non-Latinx)
- Age
- Diabetes mellitus diagnosis or A1C ≥ 6.5 (yes, no)

Additional measures may also be included.

7.2 Primary Outcome Analysis

The primary outcome is whether or not the subject has any post-randomization study-related SAEs while on study, up to and including the Visit 5 checkpoint (or the last permitted time for Visit 5, if Visit 5 was not conducted). The primary analysis of the primary outcome implicitly adopts a last-observation-carried-forward approach, in that if such an SAE is not identified it will be assumed there was no such SAE.

Safety will be assessed by descriptive reporting of the incidence proportion of study-related SAEs in each study group, with upper one-sided 95% binomial exact confidence intervals (equivalently, lower one-sided 95% binomial exact confidence intervals for the proportion without any study-related SAEs). No statistical hypothesis test is planned to assess safety, which is consistent even with large Phase III trials.

7.2.1 Additional Analyses of Primary Outcome

The primary analysis of the primary outcome implicitly adopts a last-observation-carried-forward approach. As a sensitivity analysis, it will be assumed all randomized subjects without follow-up through Visit 5 had a study-related post-randomization SAE.

The primary endpoint of presence/absence of study-related SAEs will be summarized in the ITT population for the primary analysis, but it will also be separately summarized among the subset of individuals randomized to the pAF arm who received at least one dose of pAF during the study. An exact one-sided 95% binomial confidence interval will be calculated for the proportion in this subpopulation who had at least one study-related SAE.

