4.2.3 Intention-to-Treat Population

The Intention-to-Treat (ITT) population consists of all enrolled subjects who at Visit 2 are randomized to have the study wound be treated with pAF or SOC.

In order to be randomized, the wound area must not have decreased by at least 50% at Visit 2 relative to Visit 1. Because of the infeasibility of having adjudication of imaging-software-derived wound areas in real time at Visit 2, the rectangular approximation to the wound area and/or clinician judgment will be used for the Visit 1 and Visit 2 areas to determine if the Visit 2 wound area is more than half of the Visit 1 wound area. Furthermore, the study inclusion/exclusion criteria are to be reassessed at Visit 2 to ensure the subject is still eligible for the study. Receiving investigational treatment to the wound outside of the study between Visits 1 and 2 render the subject ineligible to be randomized.

Even if a $\geq 50\%$ reduction in wound size by Visit 2 causes the subject to be ineligible for randomization of one wound to pAF/SOC, the subject will still be considered part of the enrolled population. Likewise, even if a subject is not randomized because, e.g., out-of-study investigational wound care was received after Visit 1 and before Visit 2, the subject is still considered part of the enrolled population.

There is no requirement that the subject receive the randomized treatment (e.g., that pAF be injected into the wound of somebody randomized to the pAF treatment arm) to be part of this population. Primary and secondary analyses (and exploratory analyses, unless explicitly noted otherwise) comparing the arms are to be performed according to the arm to which the subject was randomized, even if this differs from the actual treatment received.

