4.2.6 Safety Population

The safety population (SAFETY) coincides with the ITT population. The SAFETY population admits comparisons between arms.

An additional population for assessing safety will be limited to ITT participants randomized to the pAF treatment arm who received at least one pAF injection during the course of the study.

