7.6 Safety Analyses

7.6.1 Formal Safety Outcome(s)

In addition to the primary outcome (post-randomization, study-related SAEs by the time of Visit 5), there are several exploratory safety outcomes.

- Whether the subject experienced any post-randomization SAEs while on study (regardless of relatedness to study participation)
- Whether the subject experienced any post-randomization, study-related AEs while on study.
- Whether the subject experienced any post-randomization unexpected AEs while on study.

The primary outcome is whether or not the subject has any post-randomization study-related SAEs while on study, up through and including the Visit 5 checkpoint (or the last permitted time for Visit 5, if Visit 5 was not conducted). Safety will be assessed by descriptive reporting of the incidence proportion of study-related SAEs in each study group and the confidence intervals as described in Section 7.2.

Any Post-randomization SAEs The number and percentage of subjects with at least one post-randomization SAE (up through the Visit 5 checkpoint, or through the last permitted time for Visit 5, if Visit 5 was not conducted), will be summarized overall and by treatment arm for the ITT population. Because this is an ITT analysis, a note will be provided along with the summary if there are any subjects randomized to the SOC group who receive one or more pAF injections in the wound during the course of the study. If applicable, the note would state how many individuals in the SOC arm had pAF administered while on study as

well as how many such individuals had any post-randomization SAEs while on study.

As a supplementary analysis, the number and percentage of subjects with at least one post-randomization SAE will be calculated for the pAF arm among the subset of the ITT population that received at least one study administration of pAF.

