Any Post-randomization Study-related AEs The number and percentage of subjects with at least one post-randomization study-related AE (up through the Visit 5 checkpoint, or through the last permitted time for Visit 5, if Visit 5 was not conducted), will be summarized overall and by treatment arm for the ITT population. Note that AEs also include SAEs. Because this is an ITT analysis, a note will be provided along with the summary if there are any subjects randomized to the SOC group who receive one or more pAF injections in the wound during the course of the study. If applicable, the note would state how many individuals in the SOC arm had pAF administered while on study as well as how many such individuals had any post-randomization study-related SAEs while on study.

In addition, the number and percentage of subjects with at least one post-randomization study-related AE will be calculated for the pAF arm among the subset of the ITT population that received at least one study administration of pAF.

Any Post-randomization Unexpected AEs The number and percentage of subjects with at least one post-randomization unexpected AE (up through the Visit 5 checkpoint, or through the last permitted time for Visit 5, if Visit 5 was not conducted), will be summarized overall and by treatment arm for the ITT population. Note that AEs also include SAEs, and that expectedness is to be noted for each recorded AE. Because this is an ITT analysis, a note will be provided along with the summary if there are any subjects randomized to the SOC group who receive one or more pAF injections in the wound during the course of the study. If applicable, the note would state how many individuals in the SOC arm had pAF administered while on study as well as how many such individuals had any post-randomization unexpected AEs while on study.

In addition, the number and percentage of subjects with at least one post-randomization unexpected AE will be calculated for the pAF arm among the subset of the ITT population that received at least one study administration of pAF.

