7.6.2 Adverse Events

The adverse event summaries described for the interim DSMB reports will also be created after time has lapsed for all study-related data to have been acquired within the permitted

time windows. The final AE summaries may be made available to the principal investigator and study sponsor.

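### The injected safety set and its exact bound leave out SOC-assigned subjects who receive pAF, although SAP 7.6.1 provides for them (minor)

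*SAP*

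**What the plan says.** The main safety population in SAP 4.2.6 is the ITT population. Under SAP 4.2.3, comparisons between arms are made "according to the arm to which the subject was randomized, even if this differs from the actual treatment received".

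Beside it stands a set of injected subjects, always with assignment to pAF as a condition of entry:

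- SAP 4.2.6: the additional safety population is "limited to ITT participants randomized to the pAF treatment arm who received at least one pAF injection".
- SAP 7.2.1: the primary endpoint is summarized separately in "the subset of individuals randomized to the pAF arm who received at least one dose of pAF during the study", and an exact one-sided 95% binomial interval is attached to that group.
- SAP 6.1: the DSMB closed session sees adverse events for subjects "randomized to the pAF treatment arm AND received at least one study-administered pAF injection". SAP 7.6.2 carries this to the end of the study: "The adverse event summaries described for the interim DSMB reports will also be created".
- SAP 7.6.1: the supplementary count for any SAE is to be "calculated for the pAF arm among the subset of the ITT population that received at least one study administration of pAF". The counts for related and for unexpected adverse events follow the same pattern.

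SAP 7.6.1 also provides for the opposite case. Each of its three summaries gets a note "if there are any subjects randomized to the SOC group who receive one or more pAF injections". The note in the paragraph on study-related adverse events is to report "how many such individuals had any post-randomization study-related SAEs while on study".

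**The concern.** The injected set is already selected by exposure, because it drops pAF-assigned subjects who were never injected. It has therefore given up the randomized comparison, which the ITT set preserves. Requiring assignment to pAF as well protects nothing further and removes some exposed subjects from a summary of exposure.

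If a SOC-assigned subject received pAF and then had a related SAE, the event would count in the SOC proportion and bound under SAP 4.2.3 and 7.2. It would enter neither the ITT pAF-arm bound nor the injected-subset bound. Section 8 of the Protocol words its conclusion as one about the safety of the product, and SAP 8 ties progression to an absence of related SAEs in the pAF arm. Both pAF bounds would be unchanged although a pAF recipient had a related SAE.

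**Working it through.** **Inputs.** Arm sizes are 30 and 30 expected, with 28/32 to 32/28 permitted (SAP 3.2). The bound is a one-sided 95% exact binomial bound (Protocol 8, SAP 7.2). The documents give no number of SOC-assigned recipients, so one such subject is an assumption. It is also assumed that every pAF-arm subject is injected and free of related SAEs.

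**Formula.** With x subjects having an event among n, the lower bound L for the event-free proportion solves P(at most x events; n, event probability 1 − L) = 0.05.

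- For x = 0: L^n = 0.05, so L = 0.05^(1/n).
- For x = 1: L^n + n(1 − L)L^(n−1) = 0.05.
- In general, L is the 5% quantile of a Beta(n − x, x + 1) distribution.

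**The plan's own figures.** For n = 30 and x = 0, 1, 2, 3 the formula gives 90.50%, 85.14%, 80.47% and 76.14%. The Protocol table shows 90%, 85%, 80% and 76%, so it reproduces. The two-sided version gives 88.4%, 82.8%, 77.9% and 73.5% and does not match.

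**One SOC-assigned subject receives pAF.** Lower bounds in percent:

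| pAF / SOC arm | Planned pAF bounds, no event | All recipients, crossover subject event-free | All recipients, crossover subject has the only event | SOC bound, without and with that event |
|---|---|---|---|---|
| 28 / 32 | 89.85 (0/28) | 90.19 (0/29) | 84.66 (1/29) | 91.06, 86.02 |
| 30 / 30 | 90.50 (0/30) | 90.79 (0/31) | 85.59 (1/31) | 90.50, 85.14 |
| 32 / 28 | 91.06 (0/32) | 91.32 (0/33) | 86.41 (1/33) | 89.85, 84.15 |

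**Differences from the planned pAF bounds.**

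- Crossover subject event-free: 90.79 − 90.50 = 0.29 points with 30 per arm (0.34 with 28 in the pAF arm, 0.26 with 32). The all-recipient bound is slightly more favourable.
- Crossover subject has the only event: 90.50 − 85.59 = 4.91 points with 30 per arm (5.19 with 28, 4.65 with 32). The all-recipient bound is less favourable.

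Arm size hardly matters. What decides the size is whether the crossover subject has the event.

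**More crossover subjects (30 in the pAF arm).** With two recipients from the SOC arm the bound is 91.06% (0/32) or 86.02% (1/32). With three it is 91.32% (0/33) or 86.41% (1/33).

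**The case against.** The strongest reply is that the SAP already discloses these subjects. The notes in SAP 7.6.1 give the number of SOC-assigned recipients and how many had a related SAE, so a reader could compute the pooled bound. A reader might infer that the plan would hide a pAF-related event, and the documents do not support that. What is missing is a planned bound, in a descriptive analysis without a hypothesis test.

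Second, two contingencies must both occur: a SOC-assigned subject is injected, and that subject then has a related SAE. The Protocol's section on drug dispensation has pAF packed and sent when a wound is randomized to pAF, and the wording in SAP 7.6.1 is conditional. The 5 points come from placing the trial's only event in the only crossover subject. This stands, and it sets the weight of the point. SAP 3.2.2 should not be cited on either side: it concerns misrandomization, not receipt of the non-assigned treatment.

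Third, other safeguards apply. The medical monitor assesses every SAE, the DSMB sees actual assignments, and one study-level stopping criterion in the Protocol covers any subject with specified outcomes from the product. A second criterion is limited to the pAF group. These protect subjects during the trial but do not supply the bound.

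Fourth, the restricted set has a coherent use as written: it removes never-injected subjects from the pAF-arm denominator. That is fair, and SAP 4.2.6 states no purpose for the set. Adding SOC-assigned recipients keeps that use.

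Finally, simply pooling everyone injected would be too loose. A SOC-assigned subject might be injected some time after randomization, and an earlier SAE would then count against pAF. Also, SAP 6.1 and 7.6.1 limit the count to study-administered pAF, while 4.2.6 and 7.2.1 do not. Both points stand and are met in the fix.

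**Conclusion.** The point holds as a minor one. Every planned summary of injected subjects requires assignment to pAF, so no planned bound covers all recipients, although SAP 7.6.1 provides for recipients in the SOC arm. The restriction is explicit and consistent, so this is a choice of analysis set and not a contradiction.

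The size depends wholly on events that may not occur: zero without crossover, about 0.3 points in the favourable direction for one event-free crossover subject, and about 5 points in the unfavourable direction if that subject has the sole related SAE. With 30 per arm the last case lies below the Protocol's 90% figure. With 28 in the pAF arm the planned bound is already just under it (89.85%).

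A reader might go further and infer that crossover is expected, that the 90% statement is wrong, or that the primary analysis should be as treated. The documents support none of these. They give no crossover rate, the 90% figure is correct for 0 events in 30, and ITT is a sound primary analysis.

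**What to change.** In SAP 4.2.6 and 7.2.1, and where the restriction is repeated in 6.1 and 7.6.1:

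- Define the injected set as all randomized subjects who received at least one study-administered pAF injection, whatever their assigned arm. This also makes the study-administered condition uniform.
- For SOC-assigned recipients, count only events with onset on or after their first pAF injection.
- Compute the already planned exact one-sided 95% bound in this set. Report it beside the ITT pAF-arm bound when the results are used to conclude on the safety of pAF.
- Keep the ITT analysis as primary and the worst-case sensitivity analysis in SAP 7.2.1 unchanged.

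The cost is one population definition carried to the places that repeat it. SAP 7.6.1 already requires SOC-assigned recipients to be identified, and Protocol 7 already has onset dates recorded for adverse events. The downside is that the set is descriptive and not a randomized comparison, and its bound may be less favourable than the planned one. Without crossover no result changes. Settling the definition now avoids choosing it after an event is known.

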7.3 Secondary Outcome Analysis

The secondary outcome is the percentage reduction in wound area at Visit 5 relative to wound area at Visit 2. Because reduction in wound area at Visits 3 and 4 are exploratory outcomes, the general definition for deriving percent reduction in wound area at Visit k relative to Visit 2 is

$$1 - \frac{\text{Visit } k \text{ wound area}}{\text{Visit 2 wound area}} \times 100\%,$$

with all measurements expressed as the area determined through the imaging software. Wound area will be reported in (cm^2), although for purposes of the percent reduction the units are immaterial. The percent reductions will be summarized overall and by assigned treatment arm for the ITT population, using means and standard deviations or medians and interquartile ranges, as appropriate given the observed skewness and presence of extreme outliers.

The inclusion criteria limit the study to wounds which are difficult to heal, explaining why patients are not randomized if the wound area shrinks significantly between Visits 1 and 2. Therefore, any greater reduction in wound size with pAF than with SOC will suggest efficacy of pAF for wound treatment. To describe a trend in a statistical hypothesis testing framework, the following two-sided hypothesis will be assessed:

$$H_0 : \mu_{pAF} = \mu_{SOC} \text{ versus } H_1 : \mu_{pAF} \neq \mu_{SOC}.$$

Note that μ_{pAF} (μ_{SOC}) represents the average percent reduction in wound area at Visit 5 compared to Visit 2 for the pAF (SOC) treatment.

To provide an intuitive effect size, percentage change from Visit 2 will be computed at Visits 3, 4, and 5 (approximately 6, 12, and 25 weeks after randomization). If there are study visits outside of the visit's ± 1 week window, all percentages will be divided by the number of elapsed days since Visit 2, so the outcome is expressed as a percentage change per day.

If the change in wound size at Visit 5 follows a reasonably symmetric distribution within each treatment arm, then a two-sided, two-sample, unpooled t-test will be performed to compare the mean percentage reductions at Visit 5 between arms for the ITT population. If the distribution is very asymmetrical in one or both arms, a Wilcoxon rank sum test will be used. In either case, Rubin's rules will be used to combine inferences across the multiply imputed data sets and the test will be declared statistically significant if the two-sided p-value is ≤ 0.05 .

Only the wound randomized to treatment is considered for the secondary outcome. Other wounds are to receive standard-of-care and measurements on other wounds are only applicable, if at all, to exploratory analyses. See the protocol for further details.

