2.2.2 Secondary Outcome

The secondary outcome pertains to efficacy: the percentage reduction in wound area at Visit 5 relative to Visit 2.

Eligibility for Secondary Analysis The secondary outcome is to be evaluated in subjects who are randomized.

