5.2 Methods for Withdrawals, Missing Data, and Outliers

The applicability of some measures will depend on whether or not the wound is (or has previously) closed. Values that are not observed because they are not applicable will be excluded from the pertinent analyses, rather than regarded as missing. Values that are not directly obtained but are implied by other measurements will use the implied value.

Multiple imputation (MI) will be applied for analyses of the secondary outcome. Using MI leverages partial information and attempts to reduce bias in final inferences that could result from a naive complete-case analysis. A minimum of ten data sets will be generated. Chained equations will be used along with variable selection; for imputing missing values for a given variable, the input variables will be limited to those that increase the R^2 value by at least 0.01. If feasible, MI will be conducted separately within each treatment arm. The pool of variables for the imputation process includes: wound area per the imaging software at Visits 1, 2, 3, 4, and 5; treatment arm if infeasible to impute by treatment arm; and indicators for comorbidities. The following comorbidities will be considered: diabetes, peripheral vascular disease, and immunosuppression. Imputation will exclude individuals

who were not randomized.

Visit measurements obtained outside the permissible window may or may not be used in the imputation model. We will determine the closest visit number to assign the out-of-window visit per the protocol's timing for follow-up visits. The out-of-window measurement will be used for the determined visit number in the case that the visit number does not already have a valid measurement (and if there are multiple out-of-window candidate measurements, the one closest to the protocol timing will be used). Otherwise, the out-of-window measurement will be ignored.

Multiple imputation may also be used for exploratory outcomes, as appropriate.

We do not plan to use different methods for missing data due to withdrawal compared with data missing for other reasons.

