7.4 Exploratory Outcome(s) Analyses

7.4.1 Wound Area Reduction at Visits 3, 4

The percent reduction in wound area at Visit 3 (4) relative to Visit 2 will be summarized overall and by assigned treatment arm for the ITT population. If there are study visits outside of the visit's ± 1 week window, all percentages will be divided by the number of elapsed days since visit 2, so the outcome is expressed as a percentage change per day. The summary will include means and standard deviations or medians and interquartile ranges, as appropriate.

If the change in wound size at Visit 3 (4) follows a reasonably symmetric distribution within each treatment arm, then a two-sided, two-sample, unpooled t-test will be performed to compare the mean reductions at Visit 3 (4) between arms for the ITT population. If the distribution is very asymmetrical in one or both arms, a Wilcoxon rank sum test will be used.

7.4.2 Wound Area Reduction at Visits 3, 4, 5, per rectangular wound area approximation

The secondary outcome relies on wound images that are compatible for use with the imaging software. However, there is also interest in assessing reduction in wound area for wound areas calculated with the rectangular approximation. The area per rectangular approximation at visit k , $RectangularApprox_k$, is defined as:

$$RectangularApprox_k \equiv MaxWidth_k \times MaxLength_k,$$

where $MaxWidth_k$ and $MaxLength_k$ are the maximal width and length (in cm), at Visit k , respectively.

As an exploratory outcome, the percent reductions per rectangular approximation at Visits 3, 4, and 5 relative to Visit 2 will be analyzed in the same manner as for the percent reductions per imaging software. Each analysis of the rectangular wound area approximations is considered an exploratory analysis to gauge the sensitivity of the secondary outcome analysis.

7.4.3 Wound Closure at Visit 5

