7.4.7 Wound Depth Reduction

The maximal depth of the wound is scheduled to be measured at each study visit. The percent reduction in the maximal depth at Visits 3, 4, and 5 relative to Visit 2 will be calculated as $(1 - (\text{maximal depth at Visit } k) / (\text{maximal depth at Visit 2})) \times 100\%$ for $k = 3, 4, 5$. The percent reduction for these visits will be summarized overall and by treatment arm in the ITT population. The summaries for each visit number (3, 4, and 5) will use means and

standard deviations or medians and interquartile ranges, as appropriate, and will be limited at each timepoint to observations with nonmissing values. As for the wound area reduction, if any measurements are obtained outside of the permissible follow-up windows the wound depth reductions will be standardized by dividing by the number of days since Visit 2. As a sensitivity analysis, multiple imputation may be attempted to fill in missing wound depths, with summaries of the completed data sets provided, overall and by treatment arm.

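### If visits fall out of window, the secondary endpoint switches from percent reduction to percent per day, which orders closed wounds by visit date and gives an imputed Visit 5 no stated divisor

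*SAP*

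**What the plan says.** SAP 2.2.2 gives the secondary outcome as "the percentage reduction in wound area at Visit 5 relative to Visit 2". In the hypothesis of SAP 7.3, the mean for each arm "represents the average percent reduction in wound area at Visit 5 compared to Visit 2". The 54% power in SAP 8 is computed on that scale, with closed wounds scored as 100%.

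SAP 7.3 then adds that, when there are visits outside the one-week tolerance, "all percentages will be divided by the number of elapsed days since Visit 2", so that the outcome is on a per-day scale. Protocol section 8 (Secondary Endpoint) carries the same rule. SAP 7.4.1 repeats it for Visits 3 and 4 ("all percentages will be divided by the number of elapsed days since visit 2"), SAP 7.4.2 inherits it for rectangular areas, and SAP 7.4.7 extends it to depth ("As for the wound area reduction, if any measurements are obtained outside of the permissible follow-up windows").

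The main analysis uses multiple imputation. The imputation pool in SAP 5.2 is "wound area per the imaging software at Visits 1, 2, 3, 4, and 5", plus arm and comorbidities; visit day is not in it. SAP 5.2 also assigns late or early measurements to the nearest visit: "The out-of-window measurement will be used for the determined visit number", provided that visit has no valid value of its own. SAP 5.5 says: "The definitions of key derived variables will be provided in a separate dataset specifications document".

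**The concern.** Neither the hypothesis nor the power is restated per day, so an event seen during the trial decides which quantity is tested. The trigger is also loose. The text does not say whether one late visit converts all patients or only that patient, or whether a late Visit 3 or 4 converts the Visit 5 analysis. The word *all* points to everyone. A patient-by-patient reading would mix two units in one test, which is worse.

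Dividing by days suits an outcome that keeps growing with time. Percent reduction does not: it stops at 100% once the wound closes. After that, a later visit can only lower the score. Closed wounds, the best result possible, would be separated by appointment date alone, and some would fall below wounds that are still open.

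At stake are the meaning and some of the power of the one efficacy test that is not labelled exploratory. An imputed wound area also cannot be put on the per-day scale unless someone chooses a day for it.

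**Working it through.** **Visit 5 range with every visit in window.** Each window in protocol section 5 runs from the previous visit. Taking 3 months as 91 days (assumption), the nominal day is 42 + 42 + 91 = 175, the earliest is 35 + 35 + 84 = 154 and the latest is 49 + 49 + 98 = 196.

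**Effect on scores.** Score = percent reduction / days since Visit 2.
- Closed wound: 100/154 = 0.649, 100/175 = 0.571, 100/196 = 0.510 %/day. All three tie on the stated endpoint.
- Open against closed: 93/168 = 0.554 beats 100/182 = 0.549. At day 168, any reduction above 100 × 168/182 = 92.3% does so.
- Imputed 80% reduction: 80/154 = 0.519, 80/175 = 0.457, 80/196 = 0.408, depending on a day that the SAP does not state.

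**Reproducing the SAP's power.** Inputs from SAP 8: 30 per arm, closure probability 0.5 (pAF) and 0.2 (SOC), other wounds uniform on 0-100%, two-sided 0.05. A simulated Wilcoxon test (tie-corrected normal approximation) on unscaled reduction gives 54.0-54.3%, which matches the stated 54%.

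**Power under the per-day rule.** Exactly one of 60 patients is late (by 8 to 42 days, random arm; assumption) and everyone is rescaled. The documents give no distribution of visit dates, so the in-window spread is an assumption, shown as a range. Visit 5 day = 175 plus three interval deviations (normal, clipped at ±7 days, or uniform). Two healing models are used: reduction independent of visit day, and linear healing capped at 100% with closed wounds closing uniformly between days 20 and 175 (assumption). Each cell has 60,000 simulated trials.

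| Spread per interval | Independent of day: unscaled → per day | Linear healing: unscaled → per day |
|---|---|---|
| None | 54.2 → 53.8% | 54.1 → 53.9% |
| SD 1 day | 54.1 → 51.2% | 53.7 → 51.5% |
| SD 2 days | 54.0 → 49.8% | 53.5 → 50.8% |
| SD 3.5 days | 54.3 → 48.8% | 52.9 → 50.0% |
| Uniform ±7 days | 54.3 → 48.5% | 53.1 → 49.9% |

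The loss is about 2 to 6 points (2 to 3 under linear healing), and under 1 point if all other dates are identical. Getting back to about 54% would take 32 to 35 per arm. The two scales disagree on significance in 7-10% of simulated trials (about 2% with identical other dates). More late visits cost more: with reduction independent of day, uniform windows and 20% of visits assumed 14 to 42 days late, power is 45.2%.

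**What does not change.** Welch t-test power is 41.8-42.1% unscaled and 41.7-42.1% per day. Type I error with equal timing in both arms is 4.8-5.1%.

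**The case against.** *The rule is prespecified.* Both documents state it in matching words, with a trigger and a unit, and adjusting for unequal follow-up is a legitimate aim. That stands as far as disclosure goes. It does not reconcile the rule with the stated hypothesis, and division does not adjust properly for an outcome with a ceiling. Power falls even under linear healing, the case most favourable to dividing.

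*Per day may be only a reporting scale.* The sentence sits in a paragraph on interpretable effect sizes, and the next paragraph compares mean percentage reductions. This is possible but weak, because the same sentence says that the outcome itself is expressed per day. It does show that the text needs settling.

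*Late measurements are already handled.* The test in SAP 7.3 runs on multiply imputed data sets, which SAP 5.2 builds with nearest-visit assignment. This stands: that part of the remedy is a clarification.

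*The divisor may exist elsewhere.* The dataset specification under SAP 5.5 could supply one. A reader might infer that no divisor exists; the documents support only that the SAP states none. The lowest- and highest-value sensitivity analyses need none if done on the outcome scale.

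*The effect is small and rests on assumed dates.* This stands.

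A reader might also infer that this is the only formally tested efficacy endpoint. It is not: SAP 7.4.1 to 7.4.3 and 7.4.9 prescribe exploratory tests at 0.05, and the Fisher test of closure uses no day scaling.

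**Conclusion.** The point holds as a conflict between the stated endpoint and a rule in the same section, with a modest cost. On the natural reading, the tested quantity becomes percent per day, closed wounds are ordered by visit date, and Wilcoxon power drops from about 54% to about 48-52% with one late patient and the assumed date spreads. SAP 8 uses the Wilcoxon branch for its own power figure. If visits other than the late one all fall on the nominal day, almost nothing is lost.

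Three stronger readings are not supported:
- *One late visit certainly rescales all 60 patients.* The wording favours this but does not settle it. The patient-by-patient alternative would give Wilcoxon power of 51, 46, 39 or 28% with an assumed 2, 5, 10 or 20% of patients out of window. It is the less likely reading, and those figures should not set the weight of the point.
- *The rule produces false positives.* With equal timing it does not. With one arm assumed 14 days later and no true difference, the result depends on the healing model. Under linear healing and 20% closure, error is 6.6-6.8% unscaled and 6.6-7.6% per day. If reduction does not depend on visit day, the per-day error is 10-11% at 20% closure and 40-52% at 50% closure, against about 5% unscaled. The trial is unblinded, but nothing in the documents says that timing will differ by arm.
- *The trial's main conclusion is at risk.* The trial is sized on safety, and the SAP itself presents the efficacy test as describing a trend with modest power.

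**What to change.** In SAP 7.3, 7.4.1 and 7.4.7 and in protocol section 8:
- Make unscaled percent reduction for all patients the main analysis, whatever the visit timing.
- Clarify that the nearest-visit assignment in SAP 5.2, which already builds the imputed data sets, also defines the observed outcome. Impute only when no measurement can be assigned to Visit 5.
- Keep a per-day or visit-day-adjusted analysis as a sensitivity analysis only, applied to all patients, and state which elapsed day an imputed Visit 5 takes.

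The cost is SAP wording and a protocol amendment. Under protocol section 10 the amendment needs IRB approval, and FDA review if it is judged to affect scientific quality significantly. No new data are needed. The downside is that variation in visit timing stays in the outcome as noise, with a small bias if timing differs between arms (the 6.6-6.8% above, under linear healing and a 14-day shift).
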